- 3. Patients who have been treated with:
 - Intravenous (IV) immunoglobulin (Ig) within 4 weeks before randomization
 - Immunosuppressive/chemotherapeutic medications (e.g., azathioprine, cyclophosphamide, methotrexate) within 6 months before randomization
 - Natalizumab within 2 months before randomization
 - Previous treatment with lymphocyte-depleting therapies (e.g., rituximab, alemtuzumab, ofatumumab, ocrelizumab, or cladribine) within 1 year before randomization
 - Previous treatment with mitoxantrone within 6 months before randomization
 - Use of teriflunomide within 3.5 months prior to randomization, except if active washout (with either cholestyramine or activated charcoal) was done. In that case, plasma levels are required to be measured and be below 0.02 mg/L before randomization

No washout period is necessary for patients treated with dimethyl fumarate, interferon (IFN) beta, or glatiramer acetate.

Patients being treated with dimethyl fumarate, glatiramer acetate, or IFN beta at the Screening visit can continue drug intake up to the day before Day 1 of this study (i.e., there is no need for a washout period).

- 4. Patients who have been treated with systemic corticosteroids or adrenocorticotropic hormones in the past 30 days prior to the screening magnetic resonance imaging (MRI) procedure.
- 5. Patients with uncontrolled diabetes mellitus (glycosylated hemoglobin >9%) or with diabetic neuropathy.
- 6. Patients with a diagnosis of macular edema during Screening (patients with a history of macular edema will be allowed to enter the study provided that they do not have macular edema at Screening).
- 7. Patients with severe active bacterial, viral, or fungal infections.
- 8. Patients without acceptable evidence of immunity to varicella zoster virus (VZV) at randomization (See Appendix 3 for guidance on acceptable evidence of immunity and requirement for serologic testing).
- 9. Patients who have received any live or live-attenuated vaccines (including VZV, herpes simplex, or measles) within 1 month before randomization.
- 10. Patients who have received total lymphoid irradiation or bone marrow transplantation.
- 11. Patients with any unstable medical/psychiatric condition, as assessed by the primary treating physician at each site.
- 12. Patients who in the last 6 months experienced any of the following cardiovascular conditions or findings in the screening electrocardiogram (ECG): myocardial infarction, unstable angina, stroke, transient ischemic attack or decompensated heart failure requiring hospitalization or Class III/IV heart failure.

Investigational drug:

- Fingolimod (FTY720) 0.5-mg capsules for oral administration once daily
- Fingolimod (FTY720) 0.25-mg capsules for oral administration once daily

Both strengths of fingolimod capsule will be identical in appearance and will be packaged in identical bottles.

Control drug:

Glatiramer acetate 20-mg SC injection once daily.

Study design:

This is a multicenter, randomized, rater- and dose-blinded study to compare the efficacy and safety of 0.25 mg and 0.5 mg of fingolimod with glatiramer acetate 20 mg SC in patients with RRMS.

This study will consist of 3 periods:

- Screening Period: up to 45 days for all patients
- Treatment Period: 12 months of glatiramer acetate 20 mg, fingolimod 0.25 mg, or fingolimod 0.5 mg
- Follow-up Period will occur 3 months (12 weeks) after the last dose of study drug for all patients

After signing the informed consent, patients will enter the Screening Period to determine eligibility for the study. After inclusion/exclusion criteria are reviewed again and after safety assessments are conducted, patients will enter the Treatment Period and will be randomly assigned into one of three groups (for details about the randomization see Section 9.6 - Sample size calculation):

- Group 1 will receive fingolimod 0.5 mg orally once a day for up to 12 months
- Group 2 will receive fingolimod 0.25 mg orally once a day for up to 12 months

Group 3 will receive glatiramer acetate 20 mg subcutaneously once a day for up to 12 months

Patients will take their first dose of study drug at Visit 2. Thereafter, patients in each fingolimod treatment arm will take 1 capsule orally once a day for 12 months. Patients in the glatiramer acetate treatment arm will self-administer an SC injection of 20 mg of glatiramer acetate once a day for 12 months. In order to ensure patient safety 6-hour first dose monitoring procedures are to be followed for patients receiving fingolimod. First-dose monitoring is to be conducted by the primary treating physician.

Starting at Visit 3/Month 1, all visits in the Treatment Period have a visit window of ±5 days. At Visit 7/end of treatment (EOT)/Month 12, the study staff should complete the study completion electronic case report form (eCRF).

The end-of-study follow-up visit will occur 3 months (12 weeks) after the last dose of study drug administration (for patients who complete the study and for patients who prematurely discontinue the study).

Efficacy assessments:

- MS ARR
- Magnetic resonance imaging (MRI)
- •
- •

Safety assessments:

- Physical and neurological examination
- Vital sign measurements
- Laboratory evaluations
- ECG results
- Ophthalmologic examinations
- · Pulmonary function tests
- Dermatological examination
- Columbia-Suicide Severity Rating Scale

Quality of life assessments:

Patient-reported outcomes for multiple sclerosis (TSQM,

Data analysis:

The primary outcome is the ARR which is defined as the average number of confirmed relapses per year (i.e., the total number of confirmed relapses divided by the total days in the study multiplied by 365.25). For the primary analysis, the number of relapses will include all the confirmed relapses experienced during the study. The time spent in the study will correspond to the observation period for all the relapses from first dose on study drug to end of study.

The 2 doses of fingolimod will be tested hierarchically versus glatiramer acetate in a step-down procedure. For each of the 2 fingolimod doses, the null hypothesis is that there is no difference in the ARRs between patients treated with fingolimod and patients treated with glatiramer acetate versus the alternative hypothesis that there is a difference between the 2 treatment groups. The null hypothesis will be rejected if the observed P value for the between-treatment comparison is less than the significance level as specified in multiplicity adjustment procedure.

 H_{01} : $\mu_{FTY\ 0.5\ mg} = \mu_{glatiramer\ acetate}$ versus H_{A1} : $\mu_{FTY\ 0.5\ mg} \neq \mu_{glatiramer\ acetate}$

 H_{02} : μ FTY0.25 mg= μ glatiramer acetate **versus** H_{A2} : μ FTY0.25 mg $\neq \mu$ glatiramer acetate

No formal hypothesis will be tested between the 2 fingolimod doses because the study is not powered to detect a difference in treatment effect between these doses.

The hypotheses will be tested using a negative binomial regression model with log link, using treatment, number of relapses in the previous year before study enrollment, baseline EDSS, and baseline number of Gd-enhancing T1 lesions and country (or region) as covariates. In the analysis, the response variable is the number of confirmed relapses for each patient. The patient's time in the study (natural log of time in years) is used as an offset variable to obtain the ARR, adjusted for the varying lengths of patient's time in the study (time in years). The treatment effect of fingolimod doses versus glatiramer acetate will be presented as an ARR ratio with corresponding 95% confidence intervals and p values.

To adjust for multiple testing in this study, a step-down hierarchical testing procedure will be used. There are 2 hypotheses being tested (H01, H02). Because it is highly likely that the approved dose of fingolimod (0.5 mg) is more efficacious than the lower dose (0.25 mg), the approved dose of fingolimod is initially tested against glatiramer acetate at a 2-sided significance level of 0.05. Only if this initial test H01 is rejected will H02, the low dose of fingolimod, be tested against glatiramer acetate also at a 2-sided significance level of 0.05.

The sample size calculations and power considerations follow the method outlined in Keene et al., 2007 with a constant dispersion parameter k (k=0.2231). The power of the study was evaluated under various ARR assumptions and various dropout patterns based on the cumulative literature on glatiramer acetate and the Novartis data on fingolimod. The anticipated ARR for patients treated with 0.5 mg fingolimod is μ_{FTY} $_{0.5}$ mg=0.195, the ARR for those treated with glatiramer acetate is $\mu_{\text{glatiramer acetate}}$ =0.30. Therefore, the estimated ARR reduction for fingolimod 0.5 mg versus glatiramer acetate is 35%. Assuming a dropout rate of 15% based on data from this D2312 study (status Feb-2015), the total 1960 randomized patients with approximately 847 patients in the fingolimod 0.25-mg group, 615 patients in the fingolimod 0.5-mg group, and 498 patients in the glatiramer acetate 20-mg group will achieve approximately 90% statistical power for the comparison of fingolimod 0.5 mg versus glatiramer acetate at a 2-sided significance level of 0.05. This calculation takes into account that patients who discontinue prematurely from the study can participate with partial data to the primary endpoint.

Fingolimod 0.25 mg has never been studied in a clinical trial in MS. Based on PK/PD modeling results, it is anticipated that the ARR in patients treated with fingolimod 0.25 mg is approximately 15% higher than in those treated with fingolimod 0.5 mg. In line with the PK/PD modeling, the anticipated ARR in patients treated with fingolimod 0.25 mg is $\mu_{\text{FTY 0.25 mg}}$ =0.225, which corresponds to a 25% reduction in ARR in patients treated with fingolimod 0.25 mg compared to those treated with glatiramer acetate. Following the multiplicity adjustment procedure, the power to detect a 25% reduction in ARR for patients treated with fingolimod 0.25 mg compared with patients treated with glatiramer acetate is approximately 68% at a 2-sided significance level of 0.05, if the primary objective for the fingolimod 0.5-mg dose can be rejected first. A formal comparison between the two fingolimod doses is not intended, as the study is not powered for such a comparison.

The statistical software R (Version 2.13.1, open source) and the R library packages "MASS" and "PSCL" were used for sample size calculations and power analysis.

1 Introduction

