The FDA has approved the Sponsor's proposal to reduce the sample size for this study. The FDA recommended to keep the number of patients in the fingolimod (FTY720) 0.25-mg treatment arm the same and agreed to reduce the other two treatment arms by up to 50% of the original sample size. This has led to a change in the randomization ratio between the three treatment groups and as a consequence an alteration of the calculated sample size. This sample size provides approximately 90% power for the primary objective. After the introduction of protocol amendment 2, the anticipated total number of patients to be screened is reduced to approximately 2610 from original 3190 patients. A screening failure rate of 25% is anticipated (supported by the current trend in this D2312 study [status Feb 2015]) and a total of 1960 randomized patients are targeted: fingolimod 0.25 mg (total 847 patients), fingolimod 0.5 mg (total 615 patients), and glatiramer acetate 20 mg (total 498 patients), respectively.

In addition, this amendment implements modifications to the inclusion/exclusion criteria. These modifications are prompted by:

- Feedback from study investigators and consultation with the study advisory group to help widening the pool of eligible subjects
- Alignment of the protocol with fingolimod's current US prescribing information and the
 prescribing information in other countries which are within the scope of this study as this
 is a Phase IIIb study with a marketed drug

The exclusion criterion 1 related to history of malignancy was rationalized to allow inclusion of patients who are now free of the past malignancy and have no trace of malignancy for the last 5 years.

The exclusion criterion 3 related to use of previous multiple sclerosis (MS) treatments was modified bearing in mind the likely duration of pharmacodynamic (PD) action of previous therapies and the assessments inherent in the screening assessments (e.g., complete blood counts) to rule out the persistence of such PD actions. Also, the criterion was modified to introduce guidance on the washout for newly approved disease-modifying therapies namely teriflunomide and dimethyl fumarate.

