The inclusion and exclusion criteria will be assessed at Screening and Randomization Visit (before patient is randomly assigned to treatment using an interactive voice response system [IVRS]). The results of all screening assessments must be available before randomization. A subject who is under screening but has not been enrolled due to failure to meet the inclusion criteria or failure to be randomized within the specified time per protocol, may be considered for re-screening if a change in the patient's medical status or a modification of the study's eligibility criteria makes the patient potentially eligible. Re-screening will be allowed on a case-by-case basis upon approval by the study Medical Monitor. A new informed consent form should be signed in case of re-screening and a new number will be assigned to the subject. The required re-screening procedures should be discussed with the Medical Monitor.

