- 8. Patients without acceptable evidence of immunity to varicella zoster virus (VZV) at randomization (See Appendix 3 for guidance on acceptable evidence of immunity and requirement for serologic testing).
- 9. Patients who have received any live or live-attenuated vaccines (including for VZV, herpes simplex, or measles) within 1 month before randomization.
- 10. Patients who have received total lymphoid irradiation or bone marrow transplantation.
- 11. Patients with any unstable medical/psychiatric condition, as assessed by the primary treating physician at each site.

- 12. Patients who in the last 6 months experienced any of the following cardiovascular conditions or findings in the screening ECG:
 - Myocardial infarction
 - Unstable angina
 - Stroke
 - Transient ischemic attack
 - Decompensated heart failure requiring hospitalization or Class III/IV heart failure

(Additional monitoring guidelines for patients with any pre-existing cardiovascular conditions are provided in Section 5.5.5.)

- 13. Patients with history or presence of a Mobitz Type II AV block, or a third-degree AV block or sick sinus syndrome, unless patient has a functioning pacemaker.
- 14. Patients with baseline QTc interval >500 msec.
- 15. Patients receiving Class Ia (e.g., ajmaline, disopyramide, procainamide, quinidine) or Class III antiarrhythmic drugs (e.g., amiodarone, bretylium, sotalol, ibutilide, azimilide, dofetilide).
- 16. Patients with severe respiratory disease, pulmonary fibrosis, or Class III or IV chronic obstructive pulmonary disease, or with clinically significant lung pathology on chest x-ray. Patients with controlled asthma are allowed to enter the study.
- 17. Patients with any of the following hepatic conditions:
 - severe hepatic injury (Child-Pugh Class C)
 - total bilirubin greater than 2 times the upper limit of the reference range, unless in context of Gilbert's syndrome
 - conjugated bilirubin greater than 2 times the upper limit of the reference range
 - aspartate aminotransferase (AST) or alanine aminotransferase (ALT) greater than 2 times the upper limit of the reference range
 - alkaline phosphatase (AP) greater than 2 times the upper limit of the reference range
 - gamma glutamyl-transferase (GGT) greater than 2 times the upper limit of the reference range
- 18. Patients with a screening WBC count <3500/mm³ or lymphocyte count <800/mm³.
- 19. Patients with any of the following neurologic/psychiatric disorders:

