6.5.3.1 Hematology

Hematology parameter blood samples will be collected as described in Table 6-1 and will include: red blood cell count, total and differential WBC count (basophils, eosinophils, lymphocytes, monocytes, and neutrophils), platelet count, hemoglobin, hematocrit, mean corpuscular volume, mean corpuscular hemoglobin, mean corpuscular hemoglobin concentration, and red blood cell morphology. In a subset of patients CD4+, CD8+, Th17, Treg, and other T-lymphocyte subsets will be determined.

For study blinding purposes (of fingolimod arms) only the absolute counts for eosinophils, basophils, and monocytes will be communicated to sites by the central laboratory. The absolute total WBC, neutrophil, and lymphocyte counts will be measured at each visit by the central laboratory and will be blinded from the sponsor and the Investigator and will only be communicated to the site in case of a notable abnormality as defined in Appendix 1 and as per guidance in Appendix 3.

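### Section 6.5.3.1 withholds white-cell and lymphocyte counts at every visit with no exception for Screening, which conflicts with exclusion criterion 18 and with the rules that screening results be available before randomisation

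*Protocol*

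**What the plan says.** Criterion 18 in Protocol Section 4.2 excludes "Patients with a screening WBC count <3500/mm³ or lymphocyte count <800/mm³". Table 6-1 schedules haematology at Screening (Visit 1) and then not until Month 1, so Screening is the only scheduled haematology sample before the first dose. Section 5.3 has the investigator or a delegate confirm every inclusion and exclusion criterion before calling the IVRS.

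Section 6.5.3.1 sets out who sees these counts. Sites receive the absolute eosinophil, basophil and monocyte counts. For the others, the absolute total white-cell, neutrophil and "lymphocyte counts will be measured at each visit by the central laboratory and will be blinded from the sponsor and the Investigator". They "will only be communicated to the site in case of a notable abnormality as defined in Appendix 1", and the sentence then adds the guidance in Appendix 3. The section gives its purpose as blinding of the fingolimod arms.

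Four other places bear on the same counts:

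- Amendment 02, Amendment rationale: the change to criterion 3 took account of how long earlier therapies are likely to act and of "the assessments inherent in the screening assessments (e.g., complete blood counts) to rule out the persistence of such PD actions".
- Section 4 (Population): "The results of all screening assessments must be available before randomization".
- Section 6.2: baseline laboratory values should be on hand before randomisation, as part of judging eligibility.
- Appendix 3, on notable lymphopenia: blinded reporting is described for subjects randomised to fingolimod.

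**The concern.** Screening is a visit, and Section 6.5.3.1 does not exempt it. Someone who writes a laboratory reporting specification from that section would suppress the very counts that criterion 18 needs, unless they were low enough to be notable. The investigator would then have to confirm a criterion without seeing the result. The sponsor is blinded to the same counts, and the documents describe no eligibility check by the central laboratory or the IVRS that would take the investigator's place.

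What is at stake is a safety criterion at entry. Appendix 3 says that fingolimod lowers circulating lymphocytes, to an average of about 500 to 600 cells/mm³. Withholding the screening count also protects no blind, because no patient has an arm at that point.

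**Working it through.** The documents give no figure to reproduce. The check compares two sets of limits and then sets the passages side by side.

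**Inputs**

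| Count | Excluded at Screening (4.2, criterion 18) | Released to site, low side (Appendix 1) |
|---|---|---|
| White cells | below 3500/mm³ | 2.0 k/mm³ or lower, that is 2000/mm³ or lower |
| Lymphocytes | below 800/mm³ | below 200/mm³ |

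**Excludable but not released, on a literal reading**

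- White cells: above 2000 and below 3500/mm³. Release limit over exclusion limit: 2000 / 3500 = 0.57.
- Lymphocytes: 200 to 799/mm³. Release limit over exclusion limit: 200 / 800 = 0.25.

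**Could the site work the counts out from what it does receive?** Section 6.5.3.1 lists five differential cell types. The total is the sum of neutrophils, lymphocytes, monocytes, eosinophils and basophils. The site gets the last three. The total, the neutrophils and the lymphocytes are all withheld, so neither the total nor the lymphocyte count can be recovered.

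**Passages side by side**

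| Place | Screening counts visible to the investigator? |
|---|---|
| 6.5.3.1, as worded | No, unless notable |
| 6.5.3.1, stated purpose | Implies yes: there is no fingolimod arm to blind at Screening |
| Section 4 | Yes: all screening results before randomisation |
| Section 5.3 | Needed: every criterion must be confirmed |
| Section 6.2 | Yes: baseline laboratory values serve eligibility |
| Appendix 3 | Implies yes: blinded reporting is for subjects randomised to fingolimod |

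The rule as worded in 6.5.3.1 stands alone against the rest. It also differs from Appendix 3 on scope by arm: 6.5.3.1 withholds these counts without limiting the rule to patients on fingolimod, while Appendix 3 describes blinded reporting only for them.

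**The case against.** The best answer is that the literal reading fails once the section is read whole. It opens with its purpose, which is to blind the fingolimod arms. Its release sentence refers to Appendix 3, which speaks of randomised fingolimod patients. Sections 4, 5.3 and 6.2 cannot be followed without the screening counts. Section 6.5.3 says in general that results go to the sites and leaves reporting details to a laboratory manual. Section 8.1 requires monitors to verify adherence to the eligibility criteria in full, so a missing count should be noticed.

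Most of this stands as evidence of intent. It does not remove the conflict. Section 6.5.3.1 is the specific rule on who sees these counts, and it says every visit without qualification. A reader has to infer the exception from elsewhere.

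A reader might go further in three ways that the documents do not support:

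- *Criterion 18 could not be applied.* This follows only if 6.5.3.1 was carried out word for word at Screening. Sections 4 and 6.2 and Appendix 3 point the other way, and the laboratory manual is not provided.
- *The revised wash-outs depend on the hidden count.* The Amendment 02 rationale gives the likely duration of action of earlier therapies as its first ground and mentions blood counts only as an example under the second. In criterion 3 itself the wash-outs are time windows, with a plasma level for teriflunomide after active washout. None turns on a blood count.
- *Patients entering with low counts can be projected to a given level on drug.* That needs an untreated mean count, and an assumption that an individual's count falls in fixed proportion to its entry value. The documents give neither.

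**Conclusion.** The point holds as an internal inconsistency in operative text. Read as written, Section 6.5.3.1 hides screening lymphocyte counts of 200 to 799/mm³ and white-cell counts above 2000 and below 3500/mm³ from the person who must apply criterion 18. It conflicts with Sections 4 and 6.2 and with Appendix 3, which together suggest that withholding was meant to begin only after randomisation.

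The wording conflict is certain. Its practical effect is not: the documents do not show how the central laboratory reported screening counts, or how many screened patients fell in these ranges. No sample size, power or significance level depends on it. It merits correction because it touches a safety criterion at entry and is cheap to put right.

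**What to change.** In Section 6.5.3.1, state that:

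1. the withholding of white-cell, neutrophil and lymphocyte counts applies only to samples taken after randomisation;
2. its scope by treatment arm is aligned with Appendix 3, since limiting it to post-randomisation samples alone would leave the two places in disagreement about the glatiramer arm;
3. screening white-cell, neutrophil and lymphocyte counts are reported to the site in full, so that criterion 18 can be applied as Sections 4, 5.3 and 6.2 require.

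Bring the central laboratory's reporting specification into line. The thresholds in criterion 18 and Appendix 1 stay as they are. The cost is a short wording change in the protocol and in the specification, with no added test and no loss of blinding at Screening.

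SAP Section 10 gives the final number randomised as 1064, so new wording can no longer affect entry to this trial. The useful step for the report is to compare the stored screening counts with criterion 18 and list any patient below either limit among the protocol deviations. This uses data already collected.
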